## Synopsis

Title	A Phase 4 long-term follow-up study to define the safety profile of radium-223 dichloride
Short title	Radium-223 dichloride long-term follow-up program
Clinical study phase	4
Study objective(s)	
The primary objectives are to define the long-term safety profile of radium-223 dichloride (for up to 7 years after the last dose of radium-223 dichloride); to assess the incidence of leukemia, myelodysplastic syndrome, aplastic anemia, and primary bone cancer or any other new primary malignancy; to assess the incidence of bone fractures and bone associated events (e.g., osteoporosis); and, in subjects who receive cytotoxic chemotherapy, to assess the incidence of febrile neutropenia or hemorrhage during their chemotherapy treatment and for up to 6 months thereafter at a frequency based on local clinical practice.
 
Section modified by Amendments 1 and 2.

Test drug(s)	
No study treatment will be provided in this long-term follow-up study.
 
Each feeder trial investigated BAY 88-8223 (radium-223 dichloride).

Name of active ingredient	Not applicable to this follow-up study.
Dose(s)	Not applicable to this follow-up study.
Route of administration	Not applicable to this follow-up study.
Duration of treatment	Not applicable to this follow-up study.
Reference drug(s)	
Not applicable to this follow-up study.

Name of active ingredient	Not applicable to this follow-up study.
Dose(s)	Not applicable to this follow-up study.
Route of administration	Not applicable to this follow-up study.
Duration of treatment	Not applicable to this follow-up study.
Indication	As defined in the feeder trial protocols.
Diagnosis and main criteria for inclusion /exclusion	
Subject was previously enrolled in a selected company-sponsored feeder trial, and has received at least 1 dose of radium-223 dichloride or placebo in the feeder trial.
 
Written informed consent.
 
There are no exclusion criteria for this study.

Study design	Interventional single-arm Phase 4 study

Methodology	
Subjects enrolled into the study will be transferred from the selected company-sponsored feeder trials with radium-223 dichloride. Subjects, their treating health care professional, or caregiver will be contacted by telephone (face-to-face data collection is possible and will replace the telephone contact if the subject is on-site within the time window of the planned telephone contact) every 6 months (<math>\pm</math> 28 days) for 7 years (or as defined in the feeder trial protocols) following the last dose of radium-223 dichloride or placebo in the feeder trial, or until death, to determine the following:
 
 
• All radium-223 dichloride-/placebo-related adverse events (AEs) and serious adverse events (SAEs)
 
• All occurrences of leukemia, myelodysplastic syndrome, aplastic anemia, and primary bone cancer or any other new primary malignancy
 
• All bone fractures and bone associated events (e.g., osteoporosis) should be collected as either AEs or SAEs if the criteria of SAE were met, regardless of the investigator's causality assessment.
 
• Cancer treatment (including any systemic cytotoxic chemotherapy or radiotherapy for any malignancy; androgen synthesis inhibitors / androgen-receptor antagonists and radiation treatment; excluding analgesics)
 
• In subjects who receive cytotoxic chemotherapy: all occurrences of febrile neutropenia or hemorrhage during their chemotherapy treatment and for up to 6 months thereafter
 
• Survival status.
 
 
Subject data collected at other standard-of-care visits and / or contacts may be used to satisfy study-required data.
 
Section modified by Amendments 1 and 2.

Type of control	Not applicable
Number of subjects	With the currently active feeder trials, approximately 800 subjects are expected to be enrolled into this long-term safety follow-up study, but the number of subjects may increase if additional trials feed into this study.
Primary / secondary variable(s)	
The primary variables are all safety-related and include:
 
 
• Incidence and severity of radium-223 dichloride-/placebo-related AEs
 
• Incidence of radium-223 dichloride-/placebo-related SAEs
 
• Incidence of leukemia, myelodysplastic syndrome, aplastic anemia, and primary bone cancer or any other new primary malignancy
 
• Incidence of bone fractures and bone associated events (e.g., osteoporosis), regardless of investigator assessment of causality;
 
• In subjects who receive cytotoxic chemotherapy: incidence of febrile neutropenia or hemorrhage during their chemotherapy treatment and for up to 6 months thereafter at a frequency based on local clinical practice
 

Time point/frame of measurement for primary variable(s)	Up to 7 years after the last dose of radium-223 dichloride or placebo in the feeder trials, or as defined in the feeder trial protocols. Section modified by Amendments 1 and 2.
Plan for statistical analysis	
This is primarily a descriptive safety study. All subjects enrolled in this study will have received at least 1 dose of radium-223 dichloride or placebo in a selected feeder trial and will be included in the safety evaluation.
 
The incidence of leukemia, myelodysplastic syndrome, aplastic anemia, and primary bone cancer or any other new primary malignancy; the incidence of bone fractures and bone associated events (e.g., osteoporosis); and in subjects who receive cytotoxic chemotherapy, the incidence of febrile neutropenia or hemorrhage during their chemotherapy treatment and for up to 6 months thereafter, will be summarized using measures that will depend upon whether the study includes a comparator group or is a single-cohort study. Other considerations include the length of follow-up time and time-to-event methods.
 
The safety data from feeder trials and 16996 will be combined within each study for all AE summaries. For pooled analyses, all data across the selected feeder trials and 16996 will be combined by treatment groups and by treatment doses, as appropriate.
 
Additional statistical analysis will be performed as described in the 16996 statistical analysis plan (SAP), feeder trial SAPs, and /or as previously communicated to Health Authorities.
 
Section modified by Amendments 1 and 2.

## List of abbreviations

*Section modified by Amendment 2 (Section 13.2.1.11).*

AE	Adverse event
ALSYMPCA	Alpharadin in Symptomatic Prostate Cancer
BHA	Bone health agent
CRO	Clinical research organization
CRPC	Castration-resistant prostate cancer
CTCAE	Common Terminology Criteria for Adverse Events; Version 4.03
DNA	Deoxyribonucleic acid
eCRF	Electronic case report form
EDC	Electronic data capture
EU	European Union
FDA	United States Food and Drug Administration
GCL	Global Clinical Leader
GCP	Good Clinical Practice
IB	Investigator's Brochure
ICF	Informed consent form
ICH	International Conference on Harmonisation
IDMC	Independent Data Monitoring Committee
IEC	Independent ethics committee
IRB	Institutional review board
NCI	National Cancer Institute
OS	Overall survival
QoL	Quality of life
RANKL	Receptor activator for nuclear factor $\kappa$ B ligand
SAE	Serious adverse event
SAP	Statistical analysis plan
SRE	Skeletal-related event
SSE	symptomatic skeletal event
SSE-FS	symptomatic skeletal event-free survival
SUSAR	Suspected, unexpected, serious adverse reaction
US	United States

## Definitions of terms

Radium-223 dichloride The investigational product, a bone-targeting alpha particle-emitting radiopharmaceutical, is a ready-to-use solution for intravenous injection containing the drug substance radium-223 dichloride. The active moiety is the alpha particle-emitting nuclide radium-223, present as a divalent cation.

## 1. Introduction

### 1.1 Background

*Section modified by Amendment 2 (Section 13.2.1.1).*

Bone metastases are common in many solid tumors, notably those arising from the prostate, breast, and lung, as well as multiple myeloma, and may cause major morbidity including fractures, severe pain, nerve compression, and hypercalcaemia.

Regardless of the nature and location of bone metastases, the use of bone targeted treatments, including potent bone health agents (BHAs, e.g. bisphosphonates or denosumab) and bone radionuclide therapy can decrease bone pain, can decrease risk of pathologic fractures, and can improve quality of life (QoL).

Alpha particle-emitting radiopharmaceuticals represent a new class of cancer therapy for the treatment of patients with bone metastases. Unlike beta-emitting radiopharmaceuticals, alpha particle-emitting radiopharmaceuticals have a more localized action  (a range of 2 to 10 cell diameters) and are much more potent, causing double-strand deoxyribonucleic acid (DNA) breaks leading to cell death. Radium-223 dichloride (Xofigo, formerly Alpharadin) is a calcium mimetic, alpha-emitting nuclide, which selectively targets areas of increased bone turnover in bone metastases. The half-life of radium-223 is 11.4 days, allowing sufficient time for its preparation, distribution, and administration to subjects. The high-energy alpha particle radiation  results in a potent and highly localized cytotoxic effect in the target areas containing metastatic cancer cells, thereby potentially reducing exposure of surrounding normal tissues, particularly bone marrow.

#### ***Prostate cancer***

Prostate cancer has become an increasingly important health issue globally. Prostate cancer is the fifth most common tumor type worldwide, with 679,060 men diagnosed each year, and is one of the leading causes of cancer-related morbidity and death.

Prostate cancer is hormone-sensitive at the time of initial diagnosis. Although most patients with advanced metastatic disease initially respond to conventional androgen deprivation therapy with medical  or surgical  castration, the median duration of disease control has been 13 to 22 months and overall survival (OS) has been 28 to 36 months. After progression to castration-resistant disease, approximately 90% of men already have bone metastases, with all their related undesirable effects, such as pain and deterioration of health-related QoL. Patients with metastatic castration-resistant prostate cancer (CRPC) have a very limited life expectancy and most often die of their prostate cancer.

Because more than 90% of patients with CRPC are at risk for bone metastases, an agent that specifically targets this major complication of disease and provides a survival benefit represents a relevant treatment option and major therapeutic advance. Radium-223 dichloride is approved in the United States (US) and the European Union (EU; as of 2013) for the treatment of CRPC patients with symptomatic bone metastases and no known visceral metastases. Approval was based on results of the randomized Phase 3 trial Alpharadin in Symptomatic Prostate Cancer (ALSYMPCA), in which radium-223 prolonged OS and time

to first symptomatic skeletal event (SSE), versus placebo, among CRPC subjects with symptomatic bone metastases, and was generally well tolerated with low myelosuppression rates and manageable gastrointestinal adverse events (AEs).

### ***Breast cancer***

Breast cancer is the most common cancer among women worldwide, with an estimated 1.67 million new cancer cases diagnosed in 2012 (25% of all cancers).

Despite recent progress in diagnostic and therapeutic approaches of early breast cancer, a significant proportion of patients relapse following adjuvant treatment and approximately 5% of women present with metastatic disease at the time of their initial diagnosis.

The clinical presentation in the metastatic setting may range from an aggressive clinical course in patients with multiple and/or extensive organ involvement to a rather indolent clinical course in those with a solitary or only few metastatic lesions (oligometastatic disease).

Bone is a frequent site of metastatic spread, with approximately 65% to 75% of patients with metastatic breast cancer having skeletal involvement. The skeleton is the first site of distant spread in 46% to 47% of patients with breast cancer. Bone-only metastases have been reported to occur in 17% to 37% of women with metastatic breast cancer.

Due to the disrupted bone remodeling process, patients with metastatic bone lesions are at risk of increased morbidity including skeletal complications typically referred to as skeletal-related events (SREs): pathological fracture, the need for radiotherapy to bone, the need for surgery to bone, spinal cord compression, and hypercalcemia.

These events will ultimately impair the patient's QoL and functional independence.

A multidisciplinary therapeutic approach is generally recommended in patients presenting with bone metastases. Current therapeutic options include systemic therapies such as endocrine therapies, chemotherapy, and BHAs (e.g., bisphosphonates, denosumab). Local therapies such as external beam radiotherapy as well as other supportive interventions (i.e., orthopedic interventions for prevention or correction of pathological fractures) are also an important part of the therapeutic management for symptom palliation.

Patients with multiple, mainly osteoblastic lesions and pain syndrome may also benefit from treatment with radionuclide therapy. Bone-seeking radionuclides have been developed for palliation of bone pain from metastases. Metastron (strontium-89) and Quadramet (samarium-153 ethylene diamine tetramethylene phosphonate) have been approved in several countries for symptom palliation in patients with bone metastases. The bone-seeking nature of these agents results in direct delivery of beta radiation to the sites of disease. Due to the long range of the beta particles from these radioisotopes, the major dose-limiting factor with this treatment modality is toxicity to the bone marrow cells, limiting the use of these agents to pain palliation only as they have not demonstrated an OS benefit. This toxicity has seriously limited their clinical use.

### ***Multiple myeloma***

Multiple myeloma is the 3rd most prevalent blood cancer after non-Hodgkin's lymphoma and leukemia, and represents approximately 1.8% of all cancers and 2.1% of all cancer deaths.(21)

Multiple myeloma is a cancer of plasma cells, differentiated B-cell lymphocytes normally responsible for producing antibodies. In multiple myeloma, collections of abnormal plasma cells accumulate in the bone marrow, interfering with the production of normal blood cells. Most cases of multiple myeloma also feature the production of a paraprotein, an abnormal immunoglobulin fragment, such as an immunoglobulin light chain, that can cause kidney problems. Bone lesions and hypercalcemia are also often encountered.

Multiple myeloma bone lesions are due to increased osteoclast activity and reduced osteoblast function, resulting from the overexpression of RANKL (receptor activator for nuclear factor- $\kappa$ B ligand) by bone marrow stroma (22). RANKL activates osteoclasts, which reabsorbs bone. The resultant bone lesions are lytic in nature and are best seen in plain radiographs, which may show "punched-out" reabsorptive lesions (including the "pepper pot" appearance of the skull on radiography). Bone pain affects more than 70% of subjects and is the most common symptom. Myeloma bone pain usually involves the spine and ribs, and worsens with physical activity. Persistent localized pain may indicate a pathological bone fracture. Involvement of the vertebrae may lead to spinal cord compression. The breakdown of bone also leads to release of calcium into the blood, leading to hypercalcemia and its associated symptoms.

The infiltration of the bone marrow with differentiated plasma cells that cause lytic lesions in large bones and vertebrae, leading to SREs, is a characteristic of relapsed multiple myeloma. The investigation of radium-223 dichloride in an *in vivo* multiple myeloma model has shown promising bone-targeting effects as monotherapy and in combination with bortezomib.(23)

### ***All indications***

Further details on radium-223 dichloride can be found in the latest version of the Investigator's Brochure (IB), which contains comprehensive information on the study drug.

Until now, no cases of myelodysplastic syndrome or bone sarcoma have been reported from clinical studies involving radium-223 dichloride. One case of acute promyelocytic leukemia was reported from study 16544 (biopsy confirmed) which was confounded by prior exposure to docetaxel. Two cases in ALSYMPCA were reported as aplastic anemia, one in the treatment arm (biopsy confirmed), confounded by prior exposure to samarium, docetaxel, and external radiation therapy, and 1 case in the placebo arm (without confirmed biopsy). In ALSYMPCA, 12 cases of new primary malignancies were observed, 7 in the radium-223 dichloride arm (N=600) and 5 in the placebo arm (N=301).(2) No cases of radium-223 dichloride-induced cancer have been reported in completed clinical studies in follow-up of up to 3 years.

## 1.2 Study rationale

*Section modified by Amendment 2 (Section 13.2.1.1).*

This study will be conducted to define the safety profile of radium-223 dichloride to meet a US Food and Drug Administration (FDA)-mandated post-marketing requirement and a request from the German Federal Office for Radiation Protection. The key attribute of radium-223 dichloride is its specific targeting of bone with limited radiation exposure beyond the intended target. However, the proximity of the bone marrow space to site of action of radium-223 dichloride means that there is potential for radiation-induced bone marrow abnormalities. These abnormalities, including bone marrow dysplasia or new primary malignancies, may not become evident until years after the initial exposure to radium-223 dichloride; therefore, long-term follow-up is required to detect them. For this reason, the long-term safety of radium-223 dichloride will be assessed in this study, with the follow-up period extending to up to 7 years after the last dose of radium-223 dichloride or placebo.

This study originally was intended to collect long-term follow-up data from prostate cancer studies only; however, radium-223 dichloride is also being studied for other indications. In order to collect comprehensive safety information across all clinical trials with radium-223 dichloride and to allow collection of long-term safety data across indications, subjects with breast cancer and multiple myeloma will also be allowed to enter the long-term follow-up study.

## 1.3 Benefit-risk assessment

In this study, the only study evaluation is capturing of safety and survival information every 6 months (face-to-face data collection is possible and will replace the telephone contact if the subject is on-site within the time window of the planned telephone contact). As such, there is no medical risk associated with participating in this trial. The benefit of study participation is longer follow-up of the subject and thereby potentially improved detection and treatment of possible side effects related to prior treatments or signs and symptoms of the disease itself.

## 2. Study objectives

*Section modified by Amendments 1 (Section 13.1) and 2 (Section 13.2.1.2).*

The primary objectives are to define the long-term safety profile of radium-223 dichloride (for up to 7 years after the last dose of radium-223 dichloride); to assess the incidence of leukemia, myelodysplastic syndrome, aplastic anemia, and primary bone cancer or any other new primary malignancy; to assess the incidence of bone fractures and bone associated events (e.g., osteoporosis); and, in subjects who receive cytotoxic chemotherapy, to assess the incidence of febrile neutropenia or hemorrhage during their chemotherapy treatment and for up to 6 months thereafter at a frequency based on local clinical practice.

### 3. Study design

#### 3.1 Design overview

*Section modified by Amendments 1 (Section 13.1) and 2 (Sections 13.2.1.1, 13.2.1.2, and 13.2.1.9).*

When eligible, subjects will enter this follow-up study and they, their health care professional, or caregiver will be contacted via telephone (face-to-face data collection is possible and will replace the telephone contact if the subject is on-site within the time window of the planned telephone contact) at 6-month intervals ( $\pm$  28 days) to record:

- Investigator-reported radium-223 dichloride-/placebo-related AEs and related serious adverse events (SAEs);
- All occurrences of leukemia, myelodysplastic syndrome, aplastic anemia, and primary bone cancer or any other new primary malignancy;
- All bone fractures and bone associated events (e.g., osteoporosis), regardless of investigator assessment of causality
- Cancer treatment (including any systemic cytotoxic chemotherapy or radiotherapy for any malignancy; androgen synthesis inhibitors / androgen-receptor antagonists and radiation treatment; excluding analgesics);
- In subjects who receive cytotoxic chemotherapy, all occurrences of febrile neutropenia or hemorrhage during their chemotherapy treatment and for up to 6 months thereafter;
- Survival status.

Subject data collected at other standard-of-care visits and / or contacts may be used to satisfy study-required data. The current study will be terminated at the time the last remaining subject in this study has completed the 7-year follow-up assessment period (or follow-up as defined in the feeder trial protocols) or died.

This study originally was intended to collect long-term follow-up data from prostate cancer studies only; however, radium-223 dichloride is also being studied for other indications. In order to collect comprehensive safety information across all clinical trials with radium-223 dichloride and to allow collection of long-term safety data across indications, subjects with breast cancer and multiple myeloma will also be allowed to enter the long-term follow-up study.

With the currently active feeder trials, approximately 800 subjects are expected to be accrued into this long-term safety follow-up study, but the number of subjects may increase if additional trials feed into this study.

### **3.2 Primary and secondary variables**

*Section modified by Amendments 1 (Section 13.1) and 2 (Section 13.2.1.2).*

This long-term follow-up study will enroll subjects who will be transferred from selected company-sponsored trials with radium-223 dichloride (feeder trials).

The primary variables are all safety-related and include:

- Incidence of and severity of radium-223 dichloride-/placebo-related AEs
- Incidence of radium-223 dichloride-/placebo-related SAEs
- Incidence of leukemia, myelodysplastic syndrome, aplastic anemia, and primary bone cancer or any other new primary malignancy
- Incidence of bone fractures and bone associated events (e.g., osteoporosis), regardless of investigator assessment of causality
- In subjects who receive cytotoxic chemotherapy: incidence of febrile neutropenia or hemorrhage during their chemotherapy treatment and for up to 6 months thereafter at a frequency based on local clinical practice

### **3.3 Justification of the design**

This is primarily a descriptive safety study. All subjects enrolled in this study will have received at least 1 dose of radium-223 dichloride or placebo in the selected feeder trials and will be included in the safety evaluation. The subject population will include subjects treated with placebo and will therefore allow the comparison of the long-term safety profile with and without treatment with radium-223 dichloride.

The procedures chosen for the evaluation of long-term safety in this study population are consistent with the ethical standards used in studies of oncology drugs, and are appropriate for the long-term safety evaluation of subjects from the feeder trials.

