### 8.2 Analysis sets

*Section modified by Amendment 1 (Section 13.1).*

**Safety:** All subjects who have received at least 1 dose of radium-223 dichloride or placebo in the feeder trials. This safety population will be used in the analysis of all safety endpoints. Subjects will be included in the analyses according to the treatment they received.

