#### 8.3.2.1 Safety analysis

*Section modified by Amendments 1 (Section 13.1) and 2 (Section 13.2.1.2).*

Adverse events will be coded using the standard Medical Dictionary for Regulatory Activities and grouped by system organ class and preferred term. Events will be summarized by frequency and proportion of total subjects, system organ class, and preferred term.

The safety data from feeder trials and 16996 will be combined within each study for all AE summaries. For pooled analyses, all data across the selected feeder trials and 16996 will be combined by treatment groups and by treatment doses, as appropriate. Separate summaries will be given for: all events related to study drug, all events by NCI-CTCAE grade, SAEs, and AEs leading to death.

Deaths and SAEs will be summarized and listed.

The incidence of leukemia, myelodysplastic syndrome, aplastic anemia, and primary bone cancer or any other new primary malignancy; the incidence of bone fractures and bone associated events (e.g., osteoporosis); and for subjects who receive cytotoxic chemotherapy, the incidence of febrile neutropenia or hemorrhage during their chemotherapy treatment and for up to 6 months thereafter, will be summarized using statistical measures that will depend upon whether the study includes a comparator group or is a single-cohort study. Other considerations include the length of follow-up time and time-to-event methods.

Statistical measures that can be used include incidence proportion, incidence rate, and cumulative incidence (or competing risk approach). Definitions of each measure will be described in detail in the SAP.

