The key attribute of radium-223 dichloride is its specific targeting of bone with limited radiation exposure beyond the intended target. However, the proximity of the bone marrow space to site of action of radium-223 dichloride means that there is potential for radiationinduced bone marrow abnormalities. These abnormalities, including bone marrow dysplasia or new primary malignancies, may not become evident until years after the initial exposure to radium-223 dichloride; therefore, longterm follow-up is required to detect them. The ERA 223 study, a phase III randomized trial in prostate cancer participants examining radium-223 dichloride versus placebo in combination with abiraterone and prednisone (study number 15396, NCT02043678) was unblinded based on the Independent Data Monitoring Committee (IDMC) recommendation following an ad hoc independent analysis where more treatmentemergent fractures and total deaths were observed in the active treatment arm compared with the placebo arm. The IDMC also recommended that all bone fractures and bone-associated events (e.g., osteoporosis) occurring in follow-up period are to be documented regardless of investigator's causality assessment. In order to collect comprehensive safety information across all clinical trials with radium-223 dichloride, documentation of fractures (pathological and non-pathological) regardless of relationship, is also implemented in the present trial. In addition, any bone health agent taken during the study period is being collected.

The follow-up period in this study extends to up to 7 years after the last dose of radium-223 dichloride or placebo.

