4.2 Per-SAP Analysis Sets

The following analysis sets will be used for the analyses described in this SAP:

Analysis Set	Description	
Enrolled analysis set (ENR)	All participants who signed an informed consent to study 16996 will be included in the Enrolled analysis set.	
	The Enrolled analysis set will be used for reports on 16996 study disposition and study conduct.	
Safety analysis set during long-term follow-up (SAF-LTF)	All participants who have received at least 1 dose of radium- 223 dichloride or placebo in an eligible feeder trial and who have signed informed consent to 16996.	
	The Safety During Long-term Follow-Up analysis set will be used for analyses of long-term safety in study 16996.	

Additional assignment details

For summaries based on the ENR analysis set by treatment group, participants who were assigned to treatment but not treated in the feeder trial will be classified based on assigned treatment group.

Unless otherwise specified, participants who enrolled in study 16996 but did not previously participate in an eligible feeder trial will be included in the overall totals in summaries based on the ENR analysis set, but will not be included in groupings by feeder trial or treatment group.

Protocol No.: **BAY 88-8223/16996** Page: 8 of 17

5. General Statistical Considerations

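### The comparison with and without radium-223 claimed in protocol 3.3 is not secured by an analysis set that depends on survival to, and consent for, study 16996

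*Protocol*

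**What the plan says.** - **The claim.** Protocol 3.3 reasons that, because placebo-treated subjects are included, the study "will therefore allow the comparison of the long-term safety profile with and without treatment with radium-223 dichloride". The same section opens with "This is primarily a descriptive safety study".
- **The protocol's analysis.** Protocol 8.2 defines the safety set as "All subjects who have received at least 1 dose of radium-223 dichloride or placebo in the feeder trials". Protocol 8.3.2.1 adds: "The safety data from feeder trials and 16996 will be combined within each study for all AE summaries".
- **The SAP's analysis.** SAP 4.1 states that the protocol's set will not be implemented and that feeder data from patients who did not enrol will not be used. SAF-LTF (SAP 4.2) takes participants dosed in an eligible feeder trial "and who have signed informed consent to 16996". Under SAP 5.1 only follow-up data collected in 16996 are analysed, by indication, feeder study and arm. SAP 6.4.2 counts as 16996-emergent those events that arise or worsen after 16996 consent, and the summaries in 6.4.2.2 are built on these.
- **Disclosure.** SAP 7.2 lists the changed analysis sets and the dropped data combination as deviations. It does not mention the comparison claimed in 3.3.
- **Survival by treatment.** Protocol 1.1 describes ALSYMPCA as the trial "in which radium-223 prolonged OS and time" to first symptomatic skeletal event. SAP 1 reports that in ERA 223 (radium-223 or placebo with abiraterone and prednisone) more fractures and "total deaths were observed in the active treatment arm compared with the placebo arm".

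**The concern.** A participant enters SAF-LTF only by living to the 16996 consent and agreeing to take part; protocol 8.4 makes participation voluntary. Both conditions are met after randomisation and after treatment. If radium-223 alters survival in a feeder trial, or if willingness to join differs by arm, the enrolled radium-223 and placebo groups need not have the same underlying risk of malignancy or fracture, even when the feeder trial was randomised.

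At stake is how by-arm percentages are read. A difference could reflect who lived long enough and chose to enrol, and a true difference could be masked. Someone whose marrow event or fracture led to death before entry does not appear in the 16996 results. Someone with an earlier non-fatal event may appear in a listing but not in the summaries of emergent events. The planned outputs do not let a reader judge how strong the selection was.

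**Working it through.** The documents state no sample size, power or event number for this point, so there is no figure of the plan's own to reproduce. The check sets the two analyses side by side, then asks how large the selection might be.

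**1. Who is analysed**

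| | Protocol 8.2 and 8.3.2.1 | SAP 4.2, 5.1 and 6.4.2 |
|---|---|---|
| Population | all dosed in the feeder trials | dosed and consented to 16996 |
| Must be alive at 16996 consent | no | yes |
| Safety data | feeder and 16996 combined | 16996 only |
| Events summarised | from both sources | emerging after 16996 consent |

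**2. What the outputs show.** Disposition in SAP 6.1.1 begins with the ENR set, those who signed 16996 consent. No table in this SAP gives, by feeder arm, the number treated, dead before entry, or alive but not enrolled. SAP 6.1.1 does summarise follow-up from day 31 after last dose and from consent, both to the last known alive date. The difference between the two means is the mean delay from last dose to consent, less about one month. Median and range cannot be recovered that way.

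**3. Share of each arm still available (illustration).** The documents give neither feeder survival curves nor the delay to consent. Assume exponential survival with medians of 12 and 15 months. Share alive at t months = 0.5^(t/median).

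| Entry (months) | Median 12 | Median 15 | Ratio |
|---|---|---|---|
| 3 | 0.841 | 0.871 | 1.04 |
| 6 | 0.707 | 0.758 | 1.07 |
| 12 | 0.500 | 0.574 | 1.15 |
| 24 | 0.250 | 0.330 | 1.32 |
| 36 | 0.125 | 0.189 | 1.52 |

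The result depends heavily on an entry time that the documents do not state. It also measures availability, not bias: the reported percentages use enrolled participants as denominator.

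**4. Distortion of event risk (illustration).** All inputs are assumptions:
- half the patients are frail;
- frailty multiplies the death hazard by r and the event hazard by q, with (r, q) = (2, 2) or (4, 3);
- the event hazard is 0.03 per year in the non-frail;
- placebo median survival is 1 or 3 years, and this fixes the baseline death hazard h;
- entry is at t = 0.5, 1 or 2 years;
- k is the survival hazard ratio, 1 for placebo and 0.7, 1.0 or 1.3 for radium-223;
- radium-223 has no effect on the event.

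Frail share at entry: f = exp(−k·r·h·t) / [exp(−k·h·t) + exp(−k·r·h·t)]. Mean event hazard at entry = 0.03 × [1 + (q − 1)·f].

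The largest ratio occurs with median 1 year, entry at 2 years, (r, q) = (4, 3) and k = 0.7. There f = 0.126 on placebo and 0.205 on radium-223, so the ratio is (1 + 2 × 0.205) / (1 + 2 × 0.126) = 1.410 / 1.252 = 1.126. In that same case the shares alive are 0.300 and 0.401, a ratio of 1.34. This shows how far availability overstates the distortion of event risk.

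| Survival HR | Event-hazard ratio at entry | Ratio of crude 5-year percentages |
|---|---|---|
| 0.7 | 1.004 to 1.126 | 1.16 to 1.32 |
| 1.0 | 1.000 | 1.000 |
| 1.3 | 0.918 to 0.996 | 0.80 to 0.88 |

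The last column assumes 5 years of follow-up after entry. It also contains the effect of longer or shorter survival after entry, so it is not selection alone.

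**The case against.** **Objections that stand**
- The study is descriptive and no formal testing is planned, so this concerns interpretation and not an invalid test.
- Selection by rollover was always part of the design: 3.3 itself speaks of enrolled subjects. Under the 8.2 set, patients who never enrolled would still have contributed no 16996 follow-up.
- SAP 1, 5.1 and 7.2 openly declare the reduced analysis.
- The synopsis label "Interventional single-arm Phase 4 study" fits a study that gives no treatment and adds nothing to the point.
- Feeder reports, and the supplemental SAP for Health Authority reports cited in SAP 5.5, may contain some of the missing counts. They were not available to check.

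**Readings that go too far**
- A reader might infer that radium-223 is shown to change survival in the feeder trials, so the arms are not comparable, or that they are filtered in opposite directions. ALSYMPCA and ERA 223 are not named as feeders, and protocol 8.3.2 says the feeder designs differ. The point reaches only feeders with a randomised placebo arm.
- A reader might infer that the arms differ by a third to a half. That needs entry at 24 to 36 months; at 3 to 6 months the same medians give ratios of 1.04 to 1.07.
- A reader might infer that nothing shows when participants entered. The mean delay can be worked out.
- A reader might infer that patients who died before entry go unreported everywhere. The documents do not say they are missing from feeder reports.

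None of this restores the claim in 3.3 or supplies the missing denominators in this SAP.

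**Conclusion.** The point holds in a limited form. Protocol 3.3 claims a comparison that the SAP version 2 analysis no longer secures. For feeder trials with a randomised placebo arm, SAF-LTF is a post-randomisation selection, so comparability is not guaranteed. Survival differences in two sponsor trials make treatment-dependent selection plausible; they do not establish it among 16996 entrants.

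Size and direction cannot be derived from the documents. Under the stated frailty assumptions, the distortion of event hazard at entry runs from none to roughly 8% downward (0.918) or 13% upward (1.126), depending on the sign of the survival effect. Differences in consent between arms are not modelled and could add to or offset this. The defect is that the selection is invisible in the planned outputs and that SAP 7.2 does not draw the consequence for 3.3.

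**What to change.** 1. **SAP 6.1.1.** Add one table per feeder trial and arm: number treated, number and percent who died before 16996 consent, alive but not enrolled, and enrolled. Give the median and range of months from last dose to consent. Patients who never consented have no consent date, so state the cut-off used to classify them.
2. **SAP 7.2 and the CSR, and protocol 3.3 if the protocol is amended.** State that by-arm results in SAF-LTF are descriptive, are conditional on survival to and consent for 16996, and are not a randomised comparison with and without radium-223.

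The cost is one table from feeder counts that the sponsor of those trials should already hold, and a more modest stated claim. No new participant contact is needed.

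A supplementary event table in the protocol 8.2 set is not recommended. Patients who did not enrol have no 16996 follow-up. Fracture collection regardless of causality entered 16996 only with Amendment 2, and the documents do not say whether the feeder trials ascertained fractures in the same way. Such a table could mix collection rules without removing the selection.
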